## STUDY TITLE

A Multicenter, Prospective, Randomized, Double-Masked, Phase 2 Study Evaluating the Safety, Tolerability, and Efficacy of Topical AG-86893 in Patients with Pterygium

## SHORT NAME

*SURPH: a StUdy of the Response to AG-86893 in patients with Pterygium Hyperemia*

## PROTOCOL NUMBER

P2-86893-001

## STATEMENT OF COMPLIANCE

This study is to be conducted in accordance with Institutional Review Board (IRB) regulations (United States [US] 21 Code of Federal Regulations [CFR] Part 56.103) or applicable Human Research Ethics Committee (HREC), or International Ethics Committee (IEC) regulations. The investigator must obtain approval from a properly constituted HREC/IRB/IEC prior to initiating the study and re-approval or review at least annually. Allgenesis is to be notified immediately if the responsible HREC/IRB/IEC has been disqualified or if proceedings leading to disqualification have begun. Copies of all HREC/IRB/IEC correspondence with the investigator should be provided to Allgenesis.

The investigator should not implement any deviation from or changes to the protocol without approval by Allgenesis and prior review and documented approval/favourable opinion from the HREC/IRB/IEC of a protocol amendment, except where necessary to eliminate immediate hazards to study participants, or when the changes involve only logistical or administrative aspects of the study (e.g., change in monitors, change of telephone numbers).

## 1 PROTOCOL SUMMARY

### 1.1 SYNOPSIS

Title:	A Multicenter, Prospective, Randomized, Double-Masked, Phase 2 Study Evaluating the Safety, Tolerability, and Efficacy of Topical AG-86893 in Patients with Pterygium
Short Name:	SURPH: a S t U dy of the R esponse to AG-86893 in patients with P terygium H yperemia
Study Description:	
Study Hypotheses:
 

• AG-86893 has an acceptable safety profile as measured by the incidence and severity of adverse events (AEs) compared with vehicle

• At least 1 concentration of AG-86893 is effective, as measured by the mean change from baseline in conjunctival hyperemia, compared with vehicle

 
Study Design:
 

• This is a multicenter, randomized (1:1:1), double-masked, vehicle-controlled, parallel-group, dose-response (0.1% and 0.3% AG-86893) study

• Participants will administer a single eye drop of study drug 3 times daily (TID) for 28 days to the study eye

• The duration of the study is 12 weeks, with 4 weeks of treatment with study drug and 8 weeks of follow-up without medication

Objectives:	
Safety Objective:
 

• Evaluate the safety and tolerability of AG-86893 eye drops in participants with pterygium

 
Efficacy Objectives:
 

• Evaluate the dose response of AG-86893 on conjunctival hyperemia

• Evaluate the dose response of AG-86893 on pterygium vascularity, volume and vessel length (exploratory)

 
Pharmacokinetic Objective:
 

• Determine plasma concentrations of AG-86893

**Endpoints:****Safety Endpoints:**

- Changes in findings from vital signs, laboratory tests, electrocardiogram (ECG)
- Changes in findings from best-corrected visual acuity (BCVA), biomicroscopy, tear film break-up time (TFBUT), lissamine green conjunctival staining, ophthalmoscopy
- AEs
- Participant assessment of ocular symptoms, including eye dryness, burning/stinging, itching, foreign body sensation, eye discomfort, photophobia, and ocular pain

**Efficacy Endpoints:**

- Change from baseline in overall conjunctival hyperemia score at Day 28 (Primary efficacy endpoint)
- Change from baseline in overall conjunctival hyperemia score at Day 7 and Day 56 (Secondary efficacy endpoint)
- Change from baseline in conjunctival hyperemia score in the quadrant with the pterygium at Days 7, 28 and 56 (Secondary efficacy endpoints)
- Change from baseline in pterygium vascularity at Days 7, 28 and 56 (Exploratory efficacy endpoints)
- Change from baseline in pterygium volume, as assessed by AS OCT, at Days 7, 28 and 56 (Exploratory efficacy endpoints)
- Change from baseline in pterygium vessel length at Days 7, 28 and 56 (Exploratory efficacy endpoints)

**Pharmacokinetic Endpoint:**

- Concentration of AG-86893 in plasma over time

**Study Population:**

Approximately 70 adult male or female participants in good general health, with conjunctival hyperemia secondary to pterygium (score of  $\geq 2$  in the quadrant with the pterygium and  $\geq 1$  in at least 2 other quadrants) will be enrolled

**Phase:**

2

**Description of Sites/Facilities**

Approximately 12 sites

**Enrolling Participants:****Description of Study Intervention:**

AG-86893 is a sterile ophthalmic nanosuspension administered as an eyedrop. Participants will administer a single drop of study drug (AG-86893 vehicle, 0.1% AG-86893, or 0.3% AG-86893) into the study eye TID (approximately every 8 hours) for 4 weeks

**Study Duration:**

18 months

**Participant Duration:**

12 weeks from time of enrollment to completion of study

## 1.2 SCHEMA

### Day -14 to -2

#### Screening

- Informed consent
- Screen potential participants by inclusion and exclusion criteria
- Submit ocular photos OU to central reading center for qualification

### Day 1

#### Pre-randomization/ On study drug

- Review all screening laboratory findings
- Concomitant medications, concurrent procedures, vital signs
- Pregnancy test, ECG, BCVA, IOP
- Confirm that participant meets all inclusion and none of exclusion criteria
- Randomization
- Select study eye; if both eyes qualify, then the eye with higher conjunctival hyperemia score will be study eye
- AS-OCT (at selected sites), ocular photography; submit to reading center
- Biomicroscopy, TFBUT, lissamine green conjunctival staining, ophthalmoscopy
- Plasma drug monitoring (at selected sites)
- Study drug dispensing and administration
- Participant questionnaire
- AE evaluation

### Day 7

#### On study drug

- Visit conducted as a phone call, or optional in-clinic visit at the discretion of the site Investigator
- Concomitant medications, compliance assessment, concurrent procedures, participant questionnaire
- AE evaluation
- If conducted on-site: Laboratory tests (hematology with differentials, serum chemistry, urinalysis), vital signs, ocular assessments (BCVA, ocular photography, AS-OCT [at selected sites], IOP, biomicroscopy)

### Day 28 (Week 4)

#### On study drug

- Study drug administration; compliance assessment
- Concomitant medications, concurrent procedures, participant questionnaire, physical characteristics, vital signs
- Pregnancy test, ECG
- Laboratory tests (hematology with differentials, serum chemistry, urinalysis)
- Ocular assessments (BCVA, ocular photography [1 hour post-dose], AS-OCT [at selected sites], IOP, biomicroscopy, TFBUT, lissamine green conjunctival staining, ophthalmoscopy)
- Plasma drug monitoring (at selected sites)
- AE evaluation

### Day 56 (Week 8)

#### Off study drug

- Concomitant medications, concurrent procedures, participant questionnaire, vital signs
- Ocular assessments (BCVA, ocular photography, AS-OCT [at selected sites], IOP, biomicroscopy, TFBUT, lissamine green conjunctival staining)
- Plasma drug monitoring (at selected sites)
- AE evaluation

### Day 84 (Week 12)

#### Off study drug/Exit

- Concomitant medications, concurrent procedures, participant questionnaire, physical characteristics, vital signs
- Pregnancy test, ECG
- Laboratory tests (hematology with differentials, serum chemistry, urinalysis)
- Ocular assessments (BCVA, IOP, biomicroscopy, TFBUT [optional], lissamine green conjunctival staining [optional], ophthalmoscopy)
- AE evaluation

### 1.3 SCHEDULE OF ACTIVITIES

Procedures	Screening Day -14 to -2 (SCR)	Enrollment/ Baseline Visit 1, Day 1 (V1D1)	Study Visit 2 Day 7 ±3 days (V2D7) ☎*	Study Visit 3 Day 28 ±3 days (V3D28)	Study Visit 4 Day 56 ±5 days (V4D56)	Final Study Visit 5 Day 84 ±5 days (V5D84)
Informed consent	X					
Demographics	X					
Medical, smoking, alcohol and drug history a	X					
Concomitant medication	X	X	X	X	X	X
Compliance assessment b			X*	X		
Concurrent procedures	X	X	X	X	X	X
Participant questionnaire c		X c	X	X c	X	X
Physical characteristics k	X			X		X
Vital signs d	X	X	X*	X	X	X
Hematology	X		X*	X		X
Serum chemistry	X		X*	X		X
Urinalysis	X		X*	X		X
Urine pregnancy test e	X	X		X		X
ECG (12-lead)	X	X		X		X
BCVA	OU	OU	OU*	OU	OU	OU
Ocular photography f	OU	SE	SE*	SE	SE	
AS-OCT g		SE	SE*	SE	SE	
IOP	OU	OU	OU*	OU	OU	OU
Biomicroscopy	OU	OU	OU*	OU	OU	OU
TFBUT		OU		OU	OU	OU h
Lissamine green staining		OU		OU	OU	OU h
Ophthalmoscopy	OU	OU		OU		OU
Plasma drug monitoring i		X		X	X i	
Randomization		X				
Study drug j		X		X		
AE review and evaluation		X l	X	X	X	X

\* Study Visit 2 (V2D7) is a phone call follow-up but may be conducted as an optional in-clinic visit at the discretion of the Principal Investigator. Asterisked assessments will only be conducted during in-clinic visit

- a) Medical history will include history of sun exposure
- b) On Day 7, study drug bottle will be weighed and returned if the visit is conducted in-clinic. If the visit is via phone, participants will be verbally instructed to maintain compliance and use the provided diary. On Day 28, study drug will be collected after administration of last dose and study drug bottles will be weighed
- c) Participant questionnaire will be administered prior to study drug administration at Visits 1 & 28
- d) Blood pressure, pulse, temperature, and breathing rate
- e) Females of childbearing potential only
- f) Ocular photography will be submitted to central reading center for assessment of conjunctival hyperemia, pterygium vascularity and pterygium vessel length
- g) At selected sites, AS-OCT imaging will be performed and submitted to central reading center for assessment of pterygium volume
- h) Test is optional at Day 84; to be performed if test shows abnormal findings at Day 56
- i) At selected sites, blood (~10 mL) for plasma drug monitoring will be collected on Day 1 and Day 28 pre-dose and post-dose at 0.5 and 1 hour after the morning dose; on Day 56, a single sample will be collected
- j) On Day 1, study drug will be dispensed and the first dose will be administered in the clinic after all study-related procedures have been performed. On Day 28 (the last day of treatment), the morning dose will be administered in the clinic prior to all study-related procedures, except the participant questionnaire
- k) Height and weight at screening; weight only at other timepoints
- l) Participants will be questioned on AEs approximately 1 hour after IP administration

Additional examinations and unscheduled visits can be included as safety concerns arise.

AE, adverse event; AS-OCT, anterior-segment optical coherence tomography; BCVA, best-corrected visual acuity; ECG, electrocardiogram; IOP, intraocular pressure; OU, both eyes; SE, study eye; TFBUT, tear film break-up time.

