- **Plasma drug monitoring.** In a subset of at least 6 participants per study group (at select study sites), blood samples (~10 mL per sample) will be collected for monitoring the plasma concentrations of AG-86893 on Day 1 and Day 28 at pre-dose and at 0.5 and 1 hour after the morning dose from participating participants. At Day 56, a single blood sample will be collected at the study visit. Plasma drug concentrations will be measured using a validated liquid chromatography, tandem mass spectrometry assay, with a target lower limit of quantitation of 0.020 ng/mL. Allgenesis shall have full ownership rights to any biological samples derived from the study.

Unscheduled visits can be included if safety concerns arise. Additional examinations may be performed as necessary to ensure the safety and wellbeing of participants during the study. Electronic Case Report Forms should be completed for each unscheduled visit.

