3.1.5 Pharmacokinetic Measure (if applicable)

A subset of 6 participants from each treatment group will participate in a PK study to collect blood samples on the morning of Day 1 and Day 28 at pre-dose, at 0.5, 1 hour post-dose. On Day 56, a single blood sample will be collected. Plasma drug concentrations will be measured using a validated liquid

chromatography, tandem mass spectrometry assay, with a target lower limit of quantitation of 0.020 ng/mL.

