4.6 Pharmacokinetic Endpoints (if available)

Data on plasma drug concentrations, if available, will be collected for those participating in the sub-study. Pharmacokinetic endpoints include:

- Individual and mean concentration and standard deviation for Day 1, Day 28, and Day 56
- Partial Area Under the Curve (AUC_{0-1h}) on Day 1 and Day 28

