6.7 Pharmacokinetic Analyses (if data available)

Pharmacokinetic analysis, if applicable, will be based on the PK sub-population using a model-independent approach.

Drug plasma concentration data will be summarized for each dose by descriptive statistics using SAS®. AUC_{0-1h} will be estimated using linear trapezoidal method.

Individual and mean concentration at each time point, C_{max} , T_{max} , and AUC_{0-1h} , where applicable, will be presented by treatment group for Day 1 and Day 28. On Day 56 individual and mean \pm SD will be presented.

Individual and mean concentration-time curves will be presented for Day 1, and Day 28 to illustrate the dynamic change of plasma concentration from hour 0 to 1.

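### Protocol 1.3 footnote j puts the Day 28 dose ahead of every procedure except the questionnaire, yet a Day 28 pre-dose plasma sample is required in the PK subset

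*Protocol*

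**What the plan says.** Footnote j of the Schedule of Activities (Protocol 1.3) sets the order on dosing days. For Day 28, the last day of treatment, it states that "the morning dose will be administered in the clinic prior to all study-related procedures, except the participant questionnaire". For Day 1 it places the first clinic dose after all the study procedures.

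Footnote i, directly above it, covers the plasma samples at selected sites, which "will be collected on Day 1 and Day 28 pre-dose and post-dose at 0.5 and 1 hour after the morning dose". Protocol 8.2 repeats the times: "on Day 1 and Day 28 at pre-dose and at 0.5 and 1 hour after the morning dose". SAP 3.1.5 has the subset attend "to collect blood samples on the morning of Day 1 and Day 28 at pre-dose, at 0.5, 1 hour post-dose".

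Protocol 8.2 sets the size of the subset: "In a subset of at least 6 participants per study group (at select study sites"). SAP 4.6 names AUC0-1h "on Day 1 and Day 28" as a PK endpoint. Under SAP 6.7 it "will be estimated using linear trapezoidal method", and concentration curves are drawn from hour 0 to hour 1 on both days. SAP 5.5 restricts the PK population to sub-study participants with every blood sample available.

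**The concern.** Plasma drug monitoring is a Day 28 row in the Schedule of Activities, so footnote j covers it as worded, and the only exception listed is the questionnaire. A site that takes footnote j at its word doses first. It then either has no pre-dose sample or records a sample drawn after the dose as the pre-dose one.

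The sample cannot be retaken. Day 28 ends treatment, no plasma is drawn on Day 7, and the Day 56 sample is off drug. It is therefore the trial's only pre-dose sample after repeated dosing. Protocol 2.1 says that the drug's pharmacokinetics after topical use have not been evaluated in humans and makes plasma characterization an objective. What is at stake is the Day 28 AUC0-1h and, under SAP 5.5, the participant's place in the PK analysis.

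**Working it through.** The documents give no figure to reproduce here. The check compares the instructions, then sizes the consequences.

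**1. The instructions compared**

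| Day | Footnote j | Footnote i, Protocol 8.2, SAP 3.1.5 | Both possible as written? |
|---|---|---|---|
| 1 | Dose after all procedures | Draws at pre-dose, 0.5 h and 1 h | No: the 0.5 h and 1 h draws follow the dose |
| 28 | Dose before all procedures except the questionnaire | Draws at pre-dose, 0.5 h and 1 h | No: the pre-dose draw precedes the dose |

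Protocol 6.1.2 describes the clinic dose and adds no exception for the PK draw. Nothing else in the two documents reconciles the footnotes.

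**2. Weight of the time-zero value**

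With points at 0, 0.5 and 1 h, the linear trapezoid gives

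AUC0-1h = 0.5 × (C0 + C0.5)/2 + 0.5 × (C0.5 + C1)/2 = 0.25 C0 + 0.50 C0.5 + 0.25 C1.

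C0 therefore carries a quarter of the weight.

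**3. Sample missing**

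Under SAP 5.5, read literally, the participant leaves the PK population, and the Day 1 and Day 56 samples go too. In a group of 6, each loss is 1/6 = 16.7%.

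**4. Post-dose sample labelled pre-dose**

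The documents give no topical human concentrations, so two assumed cases show the range.

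*Case A: one compartment, instant absorption, steady state.* Inputs are dosing every 8 h (Protocol 6.1.2) and a plasma half-life of 10 to 15 h (Protocol 2.2, Elimination; oral drug). Set the peak to 1. The true C0 is 2^(−8/t½), C0.5 is 2^(−0.5/t½) and C1 is 2^(−1/t½). The mislabelled sample is taken at the peak, so the recorded C0 is 1.

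| Half-life | True C0 | C0.5 | C1 | True AUC | AUC with C0 = 1 | Excess |
|---|---|---|---|---|---|---|
| 10 h | 0.574 | 0.966 | 0.933 | 0.860 | 0.966 | 12.4% |
| 15 h | 0.691 | 0.977 | 0.955 | 0.900 | 0.977 | 8.6% |

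These are upper ends for this model. With slower absorption, a draw soon after the drop lies close to the true pre-dose level and the error approaches 0.

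*Case B: no half-life assumed.* Set C0.5 = C1 = 1, let the true C0 run from 0 to 1, and record C0 as 1. The true AUC is 0.75 + 0.25 C0 and the recorded AUC is 1.

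| True C0 | True AUC | Excess |
|---|---|---|
| 0 | 0.750 | 33% |
| 0.5 | 0.875 | 14% |
| 1 | 1.000 | 0% |

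**The case against.** The strongest reply is that footnote i is specific to PK, says pre-dose in terms and sits directly above footnote j. The Day 1 conflict suggests that footnote j is a loosely worded general rule, and a PK site may well follow the specific one. Protocol 8.2 also refers to the Manual of Procedures for assessment details, and that manual is not available here. This stands as far as it goes: loss of the sample is a risk, not an expected outcome. It does not remove the conflict. Footnote c already puts the questionnaire before dosing, yet footnote j still names it as an exception and does not name the PK draw.

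The stakes are also limited. The SAP treats PK as conditional on data being available, sampling is at selected sites with about 6 participants per group (one group on vehicle), and no trough endpoint is named. That stands too.

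A reader might go further in two ways that the documents do not support:

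- The Day 28 schema in Protocol 1.2 lists drug administration first and plasma monitoring near the end, which could be read as confirming a dose-first order. The schema bullets are not a time sequence: the same list puts drug administration before the questionnaire, against footnotes c and j.
- A missing Day 28 value might be thought to enter the AUC as zero and bias it downward. SAP 7.5 applies its pre-dose zero rule only to Day 1 values below the quantification limit, Protocol 9.3 rules out imputation, and SAP 5.5 leads to exclusion.

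**Conclusion.** The conflict is real and unreconciled in the documents. A site that follows footnote j on Day 28 has no valid time-zero value for the Day 28 AUC0-1h. The consequence set by the SAP, read literally, is exclusion from the PK population: 16.7% of a minimum-size group for each participant lost.

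If a post-dose sample is recorded as pre-dose, the bias in AUC0-1h is upward. It runs from about 0 to a maximum of 9% to 12% with one compartment, instant absorption and a 10 to 15 h half-life, and up to 33% if the true pre-dose level is near zero and the later levels are flat. These percentages rest on assumed profiles and an oral half-life, so they show direction and order of size only.

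The impact is conditional on which footnote a site follows and is confined to the PK subset. The primary endpoint and the sample size are unaffected.

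**What to change.** Reconcile footnotes i and j of Protocol 1.3. Naming the PK draws as exceptions to footnote j's ordering, on both Day 1 and Day 28, would bring it into line with the sampling times that Protocol 8.2 and SAP 3.1.5 already require. Dose, frequency and treatment duration are not in question.

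For samples already taken, compare recorded draw and dose times, and do not analyse a sample drawn after the dose as the pre-dose value.

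The cost is one clause in a footnote and a check of recorded times. No sample, visit or participant is added.

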### 2.1 STUDY RATIONALE

Pterygium is a wing-shaped, fibrovascular lesion on the ocular surface that usually originates from the nasal bulbar conjunctiva and extends onto the corneal limbus and beyond. Although pterygium can form nasally or temporally, the predominant form occurs at the nasal limbus. As the disease progresses, the lesion distorts the corneal topography, encroaches on the visual axis, and obscures the optical center of the cornea, causing visual impairment [1, 2].

The pathogenesis of pterygium is mostly unknown; however, multiple mechanisms have been proposed. These mechanisms include ultraviolet radiation, oxidative stress, cytokines, matrix metalloproteinases (MMPs), growth factors, cumulative DNA damage, viral infections, and anti-apoptotic factors. Growth factors can induce proliferation and/or migration of epithelial cells, fibroblasts, or vascular cells, which contribute to the formation of pterygium. These include epidermal growth factor, heparin-binding growth factor, fibroblast growth factor-2 (FGF-2), nerve growth factor, ciliary neurotrophic factor, neurotrophin 4, platelet-derived growth factor (PDGF), transforming growth factor- $\beta$ , vascular endothelial growth factor (VEGF), and insulin-like growth factor binding proteins [2-4]. FGF-2 is overexpressed in cultured fibroblasts of pterygium and is involved in the corneal healing process and neovascularization [3, 5].

Multiple stimuli, such as ultraviolet radiation, hypoxia, cytokines, and growth factors, may induce VEGF expression [2]. VEGF serves as a major proangiogenic factor, which is expressed in tears, plasma, and ocular tissues of patients with pterygium [2]. VEGF regulates its tyrosine kinase receptors (VEGFR), which increased growth, migration, and survival of the endothelial cells [6]. Elevated levels of MMPs and VEGF have been reported in the epithelial cells of a pterygium leading edge [7]. PDGF may also play a role and mediates the tyrosine kinase receptors (PDGFR $\beta$ ) in the pterygium, which stimulate VEGF transcription and recruit pericytes to neovessels. Inhibition of the PDGF signaling pathway disrupts pericyte recruitment, which results in apoptosis of VEGF signaling [6].

Patients with pterygium suffer from dry eye-like symptoms, such as redness, irritation, and blurriness. Patients also have reduced TFBI [2]. Current treatment for pterygium requires a wait-and-see observation until encroachment of the cornea, usually prompting treatment with artificial tears or lubricants until surgery is required. Some patients opt for surgical removal early for cosmetic reasons. Antimetabolites, such as mitomycin C, have been used in conjunction with surgery to minimize recurrence [1, 8], as have anti-VEGF therapies [9, 10]. However, antimetabolites have severe side effects, such as scleral necrosis, corneal perforation, corneal edema, secondary glaucoma, corneal calcification, and cataracts [11-14], and anti-VEGF monotherapies have had little success in controlling recurrence [15, 16].

Pterygium prevalence rates vary widely across the world, depending on the population and region studied. Pterygium occurs more commonly in tropical regions than in temperate climates. Incidence and prevalence rates are highest in the “pterygium belt,” which ranges from 30° north to 30° south of the equator, and lower prevalence rates are found at latitudes >40°. In tropical regions, up to 52% prevalence rates can be observed [17-19]. The prevalence rate of pterygium for Caucasians residing in urban, temperate climates is estimated at 1.2% [20]. Pterygium occurs in about 2.9% of Americans in the US [21]. The pooled prevalence rate of pterygium from 6 studies from China is 9.9% [22].

Currently, there is no approved drug for pterygium on the market. The current treatment for pterygium is surgery, but recurrence and fibrosis are major sequelae of surgery. Therefore, medical treatment for pterygium is still an unmet medical need. Allgenis' AG-86893 (nintedanib, marketed oral drug reformulated as a topical ophthalmic nanosuspension) may fill this void.

The purpose of this study is to evaluate the safety, tolerability, and efficacy of AG-86893 in patients with pterygium, and obtain preliminary data on its effect on the vasculature in the conjunctiva/pterygium. The pharmacokinetics of AG-86893 have not been evaluated in humans after topical instillation. Therefore, an objective of this study also includes the characterization of the plasma concentrations of AG-86893 following ocular administration.

